6.5 Liver function tests abnormalities

Alanine aminotransferase (ALT) and aspartate aminotransferase (AST) elevation have been described with the use of abemaciclib. Hepatic monitoring should depend on the severity and persistence of the observed laboratory test abnormalities.

Liver function tests including ALT should be monitored prior to the start of therapy, at least every 2 weeks for the first 2 months, then monthly. These tests may be ordered locally, and performed within 3 business days for each timepoint.

Management of hepatic adverse events is summarized in **Table 12**.

Table 11. General guidelines for dose adjustments and delays related to elevated liver functions tests in patients treated with abemaciclib and abemaciclib plus MK-6482.

Toxicity	Arm 1 – abemaciclib alone	Arm 2 – Abemaciclib plus MK-6482
Grade 2 AST/ALT elevation > 7 days, or recurrent grade 2 AST/ALT elevation, despite maximal supportive measures	Hold abemaciclib until resolution of toxicity or grade 1. Resume abemaciclib at lower dose level.	Hold abemaciclib and MK-6482 until resolution of toxicity to grade 1. Resume abemaciclib at lower dose level. Resume MK-6482 at lower dose level.
Grade 3 ASL/ALT elevation > 48 hours	Hold abemaciclib until resolution of toxicity or grade 1. Resume abemaciclib at lower dose level.	Discontinue MK-6482. Hold abemaciclib until resolution of toxicity to grade 1. Resume abemaciclib at lower dose level.
Grade 3 ASL/ALT elevation and serum bilirubin > 2xULN without evidence of cholestasis. Grade 4 ASL/ALT elevation	Discontinue abemaciclib.	Discontinue abemaciclib and MK-6482.

Details for hepatic monitoring depend upon the severity and persistence of observed laboratory test abnormalities. If a study patient experiences elevated ALT $5 \times$ ULN and elevated total bilirubin $2 \times$ ULN, or ALT $8 \times$ ULN, liver tests, including ALT, AST, total bilirubin, direct bilirubin, gamma-glutamyl transferase (GGT), and creatine phosphokinase (CPK), should be repeated within 48 hours to confirm the abnormality and to determine if it is increasing or decreasing. If the abnormality persists or worsens, clinical and laboratory monitoring should be initiated by the investigator, based on the hepatic monitoring tests below.

Table 12. Hepatic Monitoring Tests for a Hepatic Treatment Emergent Abnormality.

Hepatic Hematology	Haptoglobin
Hemoglobin	
Hematocrit	
RBC	
WBC	
Neutrophils, segmented and bands	
Lymphocytes	Hepatic Coagulation
Monocytes	Prothrombin Time
Eosinophils	Prothrombin Time, INR
Basophils	
Platelets	
Hepatic Chemistry	Hepatic Serologies^a
Total bilirubin	Hepatitis A antibody, total
Direct bilirubin	Hepatitis A antibody, IgM
Alkaline phosphatase	Hepatitis B surface antigen
ALT	Hepatitis B surface antibody
AST	Hepatitis B Core antibody
GGT	Hepatitis C antibody
CPK	Hepatitis E antibody, IgG
	Hepatitis E antibody, IgM
	Anti-nuclear antibody
	Anti-actin antibody
	Anti-smooth muscle antibody

Abbreviations: ALT = alanine aminotransferase; AST = aspartate aminotransferase; CPK = creatine phosphokinase; GGT = gamma-glutamyl transferase; Ig = immunoglobulin; INR = international normalized ratio; RBC = red blood cells; WBC = white blood cells.

^a Reflex/confirmation dependent on regulatory requirements and/or testing availability.

6.6 Thrombotic adverse events

Thrombotic adverse events have been reported with abemaciclib. Any study drug-related grade 3 cardiovascular, vascular or thrombotic event should lead to discontinuation of both abemaciclib and MK-6482, and initiation of appropriate supportive therapy.

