2.2.1 Activity and safety of abemaciclib

Abemaciclib demonstrated antitumor activity in multiple *in vitro* and *in vivo* human cancer models, including notably breast cancer, colorectal cancer, glioblastoma multiforme, non-small cell lung cancer. The safety of abemaciclib (LY2835219) has been evaluated in a single-arm phase 1 study involving adult patients with metastatic breast cancer, colorectal cancer, glioblastoma, melanoma, non-small cell lung cancer¹⁴. The most common grade 3 adverse events (> 10% incidence) were leukopenia (10%), neutropenia (9%), thrombocytopenia (7%), diarrhea (5%). Based on pharmacokinetic data, the recommended phase 2 dose was 200 mg po bid. Tumor responses were reported with single agent abemaciclib in this phase 1 trial for patients with breast cancer, melanoma, and non-small cell lung cancer.

The MONARCH-1 phase 2 study evaluated abemaciclib in women with advanced, ER-positive breast cancer that had progressed after 1 or 2 lines of systemic chemotherapy and demonstrated a 19.5% response rate¹⁵. Most frequent adverse events (>20%) included diarrhea (90%), fatigue (65%), nausea (64%), decreased appetite (46%), abdominal pain (39%), vomiting (35%), headaches (21%), creatinine increased (99%), white blood cell decreased (91%), neutrophil count decreased (88%), anemia (69%), platelet count decreased (41%), ALT increased (30%), AST increased (26%), hypokalemia (26%), hyponatremia (21%). Grade 3 adverse events in > 5% of patients included diarrhea (20%), fatigue (13%), white blood cell decreased (28%), neutrophil count decreased (27%), hypokalemia (5%).

Abemaciclib has been also evaluated in combination with endocrine therapy. The MONARCH-2 phase 3 study evaluated abemaciclib plus fulvestrant in patients with advanced (HR+/HER2-) breast cancer who progressed on prior endocrine therapy, demonstrating a response rate of 48% in this setting¹⁶. Frequent adverse events of abemaciclib in combination with fulvestrant included diarrhea (86%) and neutropenia (46%). Rare cases of liver function tests abnormalities (13%) and deep vein thrombosis (5%) have been reported. The MONARCH-3 study evaluated first-line combination of abemaciclib plus non-steroidal aromatase inhibitor in advanced (HR+/HER2-) breast cancer, and demonstrated an objective response rate of 59%, with a similar toxicity profile¹⁷.

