5.4 Definition of Dose-limiting Toxicity

For patients treated in arm 2, DLT will be defined as any abemaciclib or MK-6482 related toxicity resulting in discontinuation or dose reduction per the guidelines in the Section 6.2 to 6.87 within the first 28 days of treatment, for which there is no clear alternative explanation (i.e. disease related).

DLTs will be defined as any of the following events not clearly due to the underlying disease or extraneous causes:

- Any death
- Non-hematologic toxicity:
 - Grade 3 or higher
 - Hy's law cases
- Hematologic toxicity (for non-acute leukemia indications):
 - Grade 4 neutropenia for more than 7 days
 - Grade 3 or higher thrombocytopenia with clinically significant bleeding
 - Neutropenic fever

The DLT definition may exclude:

- Grade 3 nausea/vomiting or diarrhea for less than 72 hours with adequate antiemetic and other supportive care
- Grade 3 or higher electrolyte abnormality that lasts up to 72 hours, is not clinically complicated, and resolves spontaneously or responds to conventional medical interventions
- Grade 3 or higher amylase or lipase that is not associated with symptoms or clinical manifestations of pancreatitis

Patients within arm 2 who do not receive at least 80% of the intended abemaciclib plus MK-6482 doses during the first 28 days for reasons other than toxicity, will not be evaluable for DLTs and will be replaced. Once a tolerable dose combination has been determined in arm 2, patients will no longer be replaced in the study.

Dose escalation will proceed within each cohort according to **Table 4**. Dose-limiting toxicity (DLT) is defined above.

Table 4. Dose-escalation scheme

Number of Participants with DLT at a Given Dose Level	Escalation Decision Rule
0 out of 3	Enter 3 participants at the next dose level.
≥ 2	Dose escalation will be stopped. This dose level will be declared the maximally administered dose (highest dose administered). Three (3) additional participants will be entered at the next lowest dose level if only 3 participants were treated previously at that dose.

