6.2 General guidelines for dose delays and dose modifications

General guidelines for dose reductions and delays according to non-laboratory and laboratory adverse events are summarized in **Table 7** and **Table 8**, respectively. Hematologic adverse events, thrombotic adverse events, diarrhea, nausea, vomiting, liver function tests and serum creatinine abnormalities are subject to specific guidelines described in the following sections.

In the situation where an adverse event is thought to be related to both study drugs (abemaciclib, MK-6482) in arm 2, recommendation for the management of toxicities related to all study drugs should apply. In the situation where an adverse event requiring is considered related only to abemaciclib or MK-6482 in arm 2, recommendation for the management of toxicities related only to abemaciclib or MK-6482 may apply. If a patient requires omission of more than 25% of doses for one or both study drugs during a cycle for tolerability, then treatment may continue if the investigator determines the patient is receiving clinical benefit.

A cycle is defined as the planned treatment interval of 28 days plus any subsequent delay prior to start of the next cycle. A delay in the start of a cycle due to holidays, weekends, bad weather, or other unforeseen circumstances will be permitted up to 7 days and not counted as a protocol deviation. Dose omissions are allowed within a cycle. Imaging evaluations should continue on schedule regardless of treatment delays or interruptions.

Table 7. General guidelines for dose adjustments and delays related to non-laboratory toxicities in patients treated with abemaciclib and abemaciclib plus MK-6482. These guidelines do not apply to the management of thrombotic adverse events, diarrhea, nausea, and vomiting, interstitial lung disease/pneumonitis which are subject to specific guidelines reported within following sections.

Treatment Related Toxicity	Arm 1 – abemaciclib alone	Arm 2 – Abemaciclib plus MK-6482
Grade 2 toxicity > 7 days not resolving despite appropriate symptomatic treatment	Hold abemaciclib until resolution of toxicity to baseline or grade 1.	Hold abemaciclib and/or MK-6482 until resolution of toxicity to baseline or grade 1.
Grade 3 toxicity	Hold abemaciclib until resolution of toxicity to baseline or grade 1.	Hold abemaciclib and/or MK-6482 until resolution of toxicity to baseline

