	Resume abemaciclib at lower dose level.	or grade 1. Resume abemaciclib and/or MK-6482 at lower dose level.
Grade 4 toxicity	Hold abemaciclib until resolution of toxicity to baseline or grade 1. Resume with lower abemaciclib dose level.	Discontinue MK-6482. Hold abemaciclib until resolution of toxicity to baseline or grade 1. Resume with lower abemaciclib dose level.

Table 8. General guidelines for dose adjustments and delays related to laboratory toxicities in patients treated with abemaciclib and abemaciclib plus MK-6482. These guidelines do not apply to the management of hematologic, liver function tests, and serum creatinine abnormalities, which are subject to specific guidelines reported within following sections.

Toxicity	Arm 1 – abemaciclib alone	Arm 2 – Abemaciclib plus MK-6482
Any drug-related grade 3 or 4 laboratory toxicity that does not resolve within 48 hours and considered clinically significant by the investigator	Hold abemaciclib until resolution of toxicity to baseline or grade 1. Resume with lower abemaciclib dose level.	Discontinue MK-6482. Hold abemaciclib until resolution of toxicity to baseline or grade 1. Resume with lower abemaciclib dose level.

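### Section 6.6 sets a stopping rule for grade 3 cardiovascular, vascular or thrombotic events but none for grade 4, and as written it conflicts with Table 7

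*Combined protocol and SAP*

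**What the plan says.** Section 6.6 is a short paragraph without a table. It notes that thrombotic events have been reported with abemaciclib and then gives one rule: "Any study drug-related grade 3 cardiovascular, vascular or thrombotic event should lead to discontinuation of both abemaciclib and MK-6482". No other grade appears.

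Section 6.2 holds the general rules. Its text sends certain events to their own sections: "Hematologic adverse events, thrombotic adverse events, diarrhea, nausea, vomiting, liver function tests and serum creatinine abnormalities are subject to specific guidelines". The caption of Table 7, the general table for non-laboratory toxicity, repeats the carve-out: "These guidelines do not apply to the management of thrombotic adverse events, diarrhea, nausea, and vomiting, interstitial lung disease/pneumonitis". Neither sentence names cardiovascular events, or vascular events that are not thrombotic.

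Table 7 has separate rows for grade 3 and grade 4:

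- Grade 3: abemaciclib (arm 1), or abemaciclib and/or MK-6482 (arm 2), is held and then resumed at a lower level.
- Grade 4, arm 1: "Hold abemaciclib until resolution of toxicity to baseline or grade 1. Resume with lower abemaciclib dose level".
- Grade 4, arm 2: "Discontinue MK-6482. Hold abemaciclib until resolution of toxicity to baseline or grade 1. Resume with lower abemaciclib dose level".

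**The concern.** Section 6.6 covers a wider class of events than Table 7 excludes, but names only one grade. A site that follows the text can therefore find no rule, two conflicting rules, or a rule for abemaciclib that is looser at grade 4 than at grade 3.

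The risk is one the protocol itself recognizes. Section 6.6 names thrombosis as reported with abemaciclib, and Section 2.2.1, describing abemaciclib plus fulvestrant, says that cases of "deep vein thrombosis (5%) have been reported". Sections 3.2.9 and 3.2.19 admit patients with a past deep vein thrombosis or pulmonary embolism, provided that it occurred at least two weeks before treatment and anticoagulation began at least one week before.

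Three things are at stake: whether a patient is re-exposed to abemaciclib after a severe event, whether sites in a multi-center trial act alike, and whether the adverse-event summaries in Section 14.3.4 mean the same thing for every patient. That section summarizes events leading to discontinuation together with those leading to dose modification, interruption or delay. The same event could end in either outcome, depending on which page the site followed.

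**Working it through.** No arithmetic applies. The check is to trace each type of study drug-related event through the rules as written.

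| Event | Section 6.6 | Table 7 | Result |
|---|---|---|---|
| Thrombotic, grade 3 | Discontinue both drugs | Excluded by caption | One rule |
| (a) Thrombotic, grade 4 | Silent | Excluded by caption | No grade-based rule |
| (b) Cardiovascular or non-thrombotic vascular, grade 4 | Silent | Abemaciclib held, then resumed lower in both arms; MK-6482 discontinued in arm 2 | Table 7 alone applies; for abemaciclib it is looser than Section 6.6 at grade 3 |
| (c) Cardiovascular or non-thrombotic vascular, grade 3 | Discontinue both drugs | Hold, then resume lower | Two rules that disagree |

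**Is grade 3 this protocol's shorthand for grade 3 and above?** The rest of the document suggests not. Table 7 separates the two grades. Tables 8, 10 and 13 name grades 3 and 4 together. Table 11 gives grade 4 AST/ALT elevation its own rule. The DLT definition in Section 5.4 writes "Grade 3 or higher" where it means to include higher grades.

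**Does the result depend on how the two sentences are read?** Each has a literal and a generous reading, which gives four combinations:

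1. Grade 3 only in 6.6, caption literal: (a), (b) and (c) all stand.
2. Grade 3 only, caption taken to exclude the whole Section 6.6 event class: the conflict in (c) and the Table 7 rule in (b) disappear, but no grade-based rule remains at grade 4 for any event in the class.
3. Grade 3 and above, caption literal: (a) is covered by Section 6.6. At grades 3 and 4, cardiovascular and non-thrombotic vascular events then meet two rules that disagree about abemaciclib.
4. Both generous readings together: no defect, but neither is what the text says.

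**Does it reach the MTD?** Section 5.4 opens by tying DLT to discontinuation or dose reduction under the Section 6 guidelines. It then separately lists non-hematologic toxicity of grade 3 or above, and any death. A drug-related grade 3 or grade 4 event of this kind in cycle 1 is on that list whatever Section 6.6 or Table 7 says. The 3+3 count does not change.

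**The case against.** The best defense is that the intent is plain. Thrombotic adverse events is the title of Section 6.6, so the carve-out in Table 7 can be read as a pointer to everything that section covers. On that reading (b) and (c) fall away. This is a fair reading, and (b) and (c) do rest on the literal caption. It still leaves grade 4 without a rule.

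A comparator sign before grade 3 may also have been lost: Section 6.5 gives ALT multiples of the upper limit with no comparator. That is possible but not shown, since such signs survive in Sections 6.3 and 6.4. Restoring one would close (a) but would not by itself remove the conflict with Table 7.

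The protocol also has backstops. Section 5.6 removes a participant from therapy for unacceptable adverse events and requires notice to the overall PI of life-threatening ones. The introduction to Section 6 lets the investigator delay or reduce a dose at any time. A reader might infer from the gap that a patient with a grade 4 event is unprotected; these provisions show otherwise. They allow treatment to be stopped, but set no grade-based rule.

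Three further inferences are tempting and not supported:

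- That the gap disturbs the MTD. The separate grade criterion in Section 5.4 rules this out.
- That the 5% deep vein thrombosis figure measures how often the gap would matter. It comes from breast cancer patients on abemaciclib plus fulvestrant and is given without a grade. Deep vein thrombosis is thrombotic, so the figure says nothing about (b) or (c), and the share at grade 4 that (a) needs is not in the documents.
- That grade 4 handling is looser for both drugs. In arm 2, Table 7 discontinues MK-6482 at grade 4; only the abemaciclib instruction is looser.

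**Conclusion.** The point stands as an internal inconsistency that should be corrected. On the literal text there are three faults: no grade-based rule for a grade 4 thrombotic event; an abemaciclib instruction for grade 4 cardiovascular or non-thrombotic vascular events that is looser than the one at grade 3; and two conflicting instructions for those events at grade 3. At least one fault survives if either generous reading is adopted alone; only both together remove them all.

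No numerical size can be given, because the documents report no rate of these events by grade. The consequence lies in patient safety, uniform conduct and the reporting of discontinuations. It does not extend to dose finding. Which instruction is clinically right is not a question this review answers.

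**What to change.** Reconcile Section 6.6 with Table 7 and its exclusion sentence. They should define the same event class consistently, and each drug-related cardiovascular, vascular or thrombotic event at grade 3 and at grade 4 should fall under exactly one rule. The matching sentence in the text of Section 6.2 should be checked at the same time. The sponsor's clinicians decide what the rule says.

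The cost is about two amended sentences, one in Section 6.6 and one in the Table 7 caption. Sample size, assessments and analyses do not change.

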6.7 Serum creatinine elevation

Abemaciclib has been shown to increase serum creatinine due to inhibition of renal tubular transporters without affecting glomerular function (as measured by iohexol clearance). In clinical studies, increases in serum creatinine occurred within the first month of abemaciclib dosing, remained elevated but stable through the treatment period, were reversible upon treatment discontinuation, and were not accompanied by changes in markers of renal function, such as blood urea nitrogen (BUN), cystatin C, or calculated glomerular filtration rate based on cystatin C.

Patient can continue with grade 2 creatinine elevation as long as lab value is not deemed clinically significant by investigator, and as long as creatinine remains stable upon repeat testing performed within 7 days. If creatinine is deemed clinically significant, or trends upward on

repeat testing in clinically significant manner, follow dose modification table (table 8) for management of grade 3/4 lab abnormalities.

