6. DOSING DELAYS/DOSE MODIFICATIONS

Stringent inclusion and exclusion criteria as well as close monitoring of both serious and non-serious adverse events aim at ensuring the safety of the participants in this study. All AEs will be defined and graded according to the National Cancer Institute – Common Terminology Criteria for Adverse Events (NCI CTCAE) v5.0. Safety monitoring includes physical examination, laboratory assessments, as well as serial interval histories. All serious adverse events and protocol-defined events of interest will be specifically reported. Investigators and the overall PI will review adverse events on a regular basis during the study.

Dose delays and modifications will be made as indicated in the following tables. The descriptions and grading scales found in the revised NCI-CTCAE version 5.0 will be utilized for dose delays and dose modifications. A copy of the CTCAE version 5.0 can be downloaded from the CTEP website http://ctep.cancer.gov/protocolDevelopment/electronic_applications/ctc.htm.

Regarding treatment-related side effects, abemaciclib and MK-6482 have different adverse event profiles related to their therapeutic class. Some of these adverse events overlap. Management of adverse events potentially attributed to all study compounds, guidelines for dose delays or dose modifications should apply to all study drugs. If an adverse event is attributed to a specific compound, management of dose delays or modifications should be done independently.

Examples of events of particular interest, by frequency or severity, related to abemaciclib include neutropenia, diarrhea, elevated liver function tests. Examples of events of particular interest, by frequency or severity, related to MK-6482 include anemia, edema, fatigue, diarrhea, nausea.

In general, adverse events should be managed with appropriate supportive care. Dose modifications or delays have to be considered in case of unacceptable toxicity and ineffective symptomatic treatment, in order to prevent aggravation of toxicities. Decision of dose delays or reduction may occur at any time, at the discretion of the investigator. Interruption of all study compounds during a period longer than 12 weeks should lead to study discontinuation, unless specific approval by the overall PI.

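### Section 6.7 sends creatinine to Table 8, which excludes creatinine, and the unconditional arm 2 cell of Table 8 conflicts with the single-compound rule

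*Combined protocol and SAP*

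**What the plan says.** Section 6.2 of the protocol introduces the general tables and sets some toxicities aside: "liver function tests and serum creatinine abnormalities are subject to specific guidelines described in the following sections". The Table 8 caption repeats this: "These guidelines do not apply to the management of hematologic, liver function tests, and serum creatinine abnormalities". The single row of Table 8 is triggered by "Any drug-related grade 3 or 4 laboratory toxicity that does not resolve within 48 hours and considered clinically significant by the investigator". Its arm 2 cell reads "Discontinue MK-6482. Hold abemaciclib until resolution of toxicity to baseline or grade 1. Resume with lower abemaciclib dose level".

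Section 6.7 deals with creatinine and opens with a mechanism: "Abemaciclib has been shown to increase serum creatinine due to inhibition of renal tubular transporters without affecting glomerular function". It lets a patient with a grade 2 elevation stay on treatment if the value is judged not clinically significant and is stable when retested within 7 days. If the value is clinically significant, or climbs to that degree on retest, sites are to "follow dose modification table (table 8) for management of grade 3/4 lab abnormalities".

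On attribution, the opening text of section 6 says: "If an adverse event is attributed to a specific compound, management of dose delays or modifications should be done independently". Section 6.2 is weaker. When one drug alone is blamed in arm 2, it permits the single-drug recommendation but does not require it.

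Section 6.5 opens: "Alanine aminotransferase (ALT) and aspartate aminotransferase (AST) elevation have been described with the use of abemaciclib". It says nothing either way about MK-6482. For grade 3 AST/ALT elevation lasting more than 48 hours, the arm 2 cell of Table 11 stops MK-6482 and restarts abemaciclib at a lower level.

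**The concern.** Two things do not fit together. The first is scope: the creatinine section relies on a table that says it does not cover creatinine, and the table's trigger does not match the grade 2 values that 6.7 discusses. The second is action: if Table 8 is used, its arm 2 cell stops MK-6482 whatever the attribution, while section 6 tells the site to manage each compound separately when one is responsible.

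What is at stake is consistent treatment in a small arm. Two sites with the same arm 2 patient could do different things with MK-6482, each citing the protocol. Section 5.4 also counts drug-related toxicity that leads to discontinuation or dose reduction under section 6.2 onward in the first 28 days as a DLT, and 6.7 says the creatinine rise appears in the first month. Uncertainty about which rule applies could therefore reach the DLT count, and through it the MTD, a co-primary endpoint of arm 2.

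**Working it through.** No formula applies. The check sets the passages side by side and follows each reading to its result.

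**Step 1, scope.** Section 6.2 and the Table 8 caption send creatinine to a later, specific section. That section is 6.7, and 6.7 sends the qualifying values back to Table 8. No exception in the caption allows for this.

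**Step 2, trigger.** The Table 8 row needs grade 3 or 4, drug-related, unresolved after 48 hours and clinically significant. Section 6.7 can send a grade 2 value there. Read literally, the row does not cover it.

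**Step 3, action in arm 2.** The cell gives MK-6482 a stop with no restart step, and gives abemaciclib a hold and a restart at a lower level. Section 6.7 names only abemaciclib as a cause, and the frequent MK-6482 events in section 7.1.2 do not include creatinine. Under section 6, an event attributed to abemaciclib alone would leave MK-6482 outside the modification.

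**Step 4, comparison with other tables.** The arm 2 cells for grades 2 and 3 in Table 7, and those in Tables 9a and 9b, let the site hold one drug or both, which leaves room for attribution. The Table 8 cell and the Table 11 row cited above do not.

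**Step 5, consequence for DLTs.** Each reading is followed for a drug-related cycle 1 creatinine event in arm 2 that is clinically significant and, for grade 3 or higher, unresolved after 48 hours:

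| Grade | Reading | MK-6482 | Abemaciclib | DLT under 5.4 |
|---|---|---|---|---|
| 2 | Table 8 applies, cell as written | Stopped | Held, then lowered | Yes, first paragraph |
| 2 | Table 8 applies, managed as abemaciclib-only | Kept | Held, then lowered | Yes, first paragraph |
| 2 | Table 8 does not apply (caption, or row limited to grade 3 or 4) | No tabulated action | No tabulated action | Not by any stated rule |
| 3 or higher | Table 8 applies, cell as written | Stopped | Held, then lowered | Yes |
| 3 or higher | Table 8 applies, managed as abemaciclib-only | Kept | Held, then lowered | Yes |
| 3 or higher | Table 8 does not apply | No tabulated action | No tabulated action | Yes, separate grade criterion |

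Stopping or keeping MK-6482 never changes the last column, because abemaciclib is lowered in both cases. Only the question whether Table 8 applies changes it, and in this table only at grade 2, because 5.4 separately lists non-hematologic toxicity of grade 3 or higher. Section 6 also allows discretionary reductions at any time, but that text precedes 6.2, where the range cited in 5.4 begins.

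**Step 6, size.** Under Table 4, one added DLT moves a cohort from 0 of 3 (escalate) to 1 of 3 (enter at least 3 more), and two or more stop escalation. How often this would arise is not given. Sections 2.2.1 and 7.1.1 report increased creatinine in 99%, ALT in 30% and AST in 26% on abemaciclib alone. Those are any-grade rates, and the accompanying lists of grade 3 events above 5% name none of the three.

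**The case against.** The best reply is that 6.7 is the specific section to which the caption refers, and that it borrows the action of Table 8 for a defined subset. A specific rule that adopts a general table still ends in one action, so the caption merely lacks an exception. Section 6.7 also describes Table 8 as the table for grade 3 and 4 abnormalities, so the sponsor may have meant a worrying grade 2 value to be handled as if it were higher. Stopping MK-6482 while restarting abemaciclib appears in Table 7 (grade 4), Table 8 and Table 11, which suggests intent. And sections 6 and 6.2 already let the investigator attribute.

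Much of this stands. Borrowing is the more natural reading of 6.7, and the asymmetry between the drugs may be a deliberate clinical choice. But the exclusion is written twice without exception, the trigger still does not match, and nothing says whether an unconditional cell or the attribution rule prevails.

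Several stronger inferences are tempting, and the documents do not support them:

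- A reader might infer that any creatinine rise due to abemaciclib stops MK-6482. Section 6.7 describes a stable rise without changes in markers of renal function, and sends only clinically significant or climbing values to Table 8.
- A reader might infer that the attribution conflict changes DLT status. It does not, as Step 5 shows.
- A reader might infer that the plan blames AST/ALT rises on abemaciclib alone. Section 6.5 does not exclude MK-6482.
- A reader might infer that the combination ORR is wrongly computed if it keeps patients whose MK-6482 was stopped. The Full Analysis Set in 14.3.1 deliberately keeps every eligible patient who received a dose, so this is the stated analysis.

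**Conclusion.** The plan is inconsistent as written, and the severity is minor to moderate. Two conflicts stand: 6.7 against the Table 8 caption, trigger and section 6.2; and the unconditional arm 2 cell of Table 8 against the single-compound rule in section 6, which 6.2 restates only permissively. The Table 11 row is a weaker case of the second conflict, because it matters only when an investigator attributes the AST/ALT event to abemaciclib alone.

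The practical effect is that MK-6482 could be stopped or kept in the same arm 2 patient. The effect on the DLT count is narrower: it turns on whether Table 8 reaches creatinine at all, chiefly for grade 2 elevations in cycle 1. No number of affected patients can be given, and the 99%, 30% and 26% figures should not be used for one.

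The conclusion assumes that the stop in Table 8 has no restart, an inference from the contrast with the hold-and-resume wording for abemaciclib. It also assumes that a dose reduction under Table 8 counts under the first paragraph of 5.4, whose section range ends in a misprinted number.

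**What to change.** Reconcile 6.7 with the Table 8 caption, section 6.2 and the Table 8 trigger, so that exactly one rule governs creatinine and it is explicit whether a grade 2 value can fall under it. Reconcile the arm 2 cells of Tables 8 and 11 with the single-compound rule in sections 6 and 6.2 by stating which takes precedence when an event is attributed to one drug. Which rule is intended is for the sponsor's clinical team to decide.

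The cost is a wording amendment to a few passages and two tables. It needs no extra patients, procedures or analyses.
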